8.5.3. Follow-up Phase

For each subject, after treatment, there would be two follow-up visits (Visit 6-7) in one year, one visit every 6 months (month 18 and 24).

- Concomitant medications (a window period of 28 days prior to the start of the study treatment, during the study and up to 28 days post the last dose of treatment applies).
- Adverse Events Assessment.
- Update in Disease Status (including PFS, RR, TTR, TTF, OS).
- Update in Treatment Status/ Change in therapy.
- Reporting of routine labs collected.

- Performance Status (ECOG), weight (BMI) and blood pressure.
- QOL questionnaire (FKSI 19) ([Appendix 1](#)).

In case of no treatment failure till month 12, more treatment visits will be scheduled until SU discontinuation.

8.6. Data Sources

Data will be collected in routine clinical practice and from medical records as the inclusion criteria (Patients being treated with SU in 1st line according to the approved therapeutic indication) and the medication are prescribed within the regular practice of the physician. As a non-interventional study, there are no specific requirements in regards to the treatment process.

A case report form (eCRF) will be used for data collection. The eCRF must be signed by the investigator. The signatures serve to attest that the information contained on the eCRFs is true. At all times the investigator has the final personal responsibility for the accuracy and authenticity of all clinical and laboratory data entered into the eCRFs.

An investigator performs an assessment of new or ongoing adverse events, relative to a patient's baseline history, at each study visit. Generally, the identification of new or ongoing adverse events is determined till the last scheduled visit.

8.7. Sample Size

Due to the non-existence of a sample size calculation/justification for estimating the median progression free survival in phase IV trials and the exploratory/observatory nature of this study, we opt not to base the sample size on the main objective. However, we will use the secondary objective of estimation of the ORR for adv/mRCC patients receiving SU in the 1st line as the basis of the sample size. With 140 patients we will be able to assess the ORR to within a margin of error of at most $\pm 8\%$ using 95% confidence intervals. This is based on the assumption that the ORR will be less than 37% as per the literature.^{12,25} This sample size is also within the range of sample sizes of other studies investigating SU for first line and where PFS and TTF were estimated.²⁵

The 140 patients will be enrolled at 14 sites in the Middle Eastern & African countries; namely UAE, Qatar, RSA, Egypt, Algeria, Tunisia and Morocco. Each site is expected to enroll an average of 10 patients. This will ensure diverse and possibly representative sample of the Middle East and North Africa region.

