3.3.3. End-points

Primary End-point:

1. Progression Free Survival (PFS) for patients with ad/mRCC receiving SU.

PFS is defined as: the time from when the patient receives the first dose of SU to the time of progression or death due to any cause, which occurs first.

2. Time to Treatment Failure (TTF) for SU 1st line.

TTF is defined as: from when the patient receives the first dose of SU to the time of SU discontinuation (date completed by the physician).

Secondary End-point:

1. Objective Response Rate (OOR) for adv/mRCC patients receiving SU as 1st line treatment.

ORR is defined as the percentage of patients with confirmed CR or confirmed PR according to RECIST criteria v1.1.

2. Description of SU real life usage of doses across all centers, including description of treatment schedules (dose change, dose schedule, average dose received during the period treatment).

3. Combined PFS for patients with ad/mRCC receiving the 2nd line sequence SU- different treatment.

Combined PFS is defined as: the time from when the patients receives the first dose of SU as first line, until progression or death due to any cause while on the 2nd line treatment, whichever occurs first during the 2nd line sequence treatment.

4. Combined TTF for the SU-2nd line sequence.

Combined TTF is defined: as the time from when the patient receives the first dose with SU as first line, to the time of 2nd line sequence discontinuation (date completed by the physician).

5. OS for adv/mRCC patients receiving SU as first line followed by 2nd line as measured from date of first SU dose to the date of death of any cause. The OS median and the overall survival at month 24 (24 months OS) will be measured.
6. If possible, efficacy parameters (PFS, OS) for the combined 1st line SU- 2nd line sequences according to the second line post SU (other than SU-AXI):
 - SU in 1st line-Axitinib TKI in 2nd line.
 - SU in 1st line- other TKI in 2nd line (sorafenib, pazopanib).
 - SU in 1st line/mTOR in 2nd line (temsirolimus, everolimus).
7. Safety description with AE listing in patients receiving SU: frequencies of patients experiencing at least one AE will be displayed by body system.
8. QoL using the questionnaire Functional Assessment of Cancer Therapy-Kidney Symptom Index 19 (FKSI-19).

CCI

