8.9. Data Analysis

Detailed methodology for summary and statistical analyses of data collected in this study will be documented in a Statistical Analysis Plan (SAP), which will be dated, filed and maintained by the sponsor. The SAP may modify the plans outlined in the protocol; any major modifications of primary endpoint definitions or their analyses would be reflected in a protocol amendment.

Demographic and other clinical characteristics of the patients will be summarized using the mean, standard deviation, median, minimum, and maximum values, for numeric variables such as age and duration of follow up and frequency distributions for categorical data such as gender. The median and 95% confidence intervals for the main outcomes PFS and TTF will be estimated using the method of Kaplan-Meier. The ORR for adv/mRCC patients receiving SU in the 1st line will be computed along with its 95% confidence interval using the Clopper-Pearson formula. Cox proportional hazard models may be used to explore the potential influences of baseline characteristics on PFS or TTF. A multiple logistic regression model can be used to assess the effect of prognostic variable on ORR.

Change in other variables such as Quality of life and weight at last visit as compared to the baseline will be assessed using the paired t-test at each visit in addition to computing mean differences along with 95% confidence intervals. Moreover, repeated methods can be used to look for trends over time and adjust for possible confounders.

All AEs occurring during the study will be considered as treatment-emergent, and the frequency of AEs will be summarized. Sub-group analyses of association between efficacy outcomes, safety measurements, and baseline factors will be performed for exploratory reasons as needed.

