5.5. Covariates

- In case of multivariate analyses, baseline characteristics will possibly be used as covariates.
- The final covariates will be selected according to the selection strategy of variables defined in the part 7.6.
- Possible, but not exclusive, baseline covariates related to SU initiation will be limited because of a retrospective part of the data collection, with:
 - Age and sex;
 - ECOG (0, 1, 2, 3, 4), Karnofsky performance status
 - MSKCC risk factors (Favorable, Intermediate, Poor)

- Medical history of hypertension (Yes, No)
- Delay from diagnosis (< 1 year from diagnosis to first metastasis detection/ \geq 1 year)
- Nephrectomy (Yes, No)
- Number of metastatic sites
- The covariates identified previously will be also explored and act as baseline for second line treatment initiation. In this case, other covariates will be:
 - The response to SU treatment in 1st line;
 - Duration of SU treatment, PFS;
 - Previous treatments for primary tumor (surgery, radiotherapy, other);
 - Additional anti-tumor treatments;

6. Handling missing values

- The majority of data will be collected with a website (except for FKSI-19 questionnaires).
- In this website, the input of certain data will be obligatory, limiting the number of missing values, particularly for endpoints.
- Regarding the descriptive analyses of each variable, it will be based on the available data (“observed-case analysis”), considering missing data as non-informative.
- The number of missing data will be documented for each analysis.
- The analysis of the primary endpoint is a survival analysis which is known to efficiently handle missing data: All patients are included in the analysis and missing data are called right-censored data.
- In case of absence of 20% data and over, for a main parameter such as ORR rate, the Hot-deck imputation method could be used. With this method, the missing value is replaced by the observed value of a patient with similar characteristics $X_1, X_2 \dots X_k$. If it does not exist such similar patient, the missing value will be amputated
- A sensitivity analysis will be conducted by the imputation of extreme values. In the one hand, analysis in the most unfavorable situation (i.e. missing data considered as failure) and in the other hand, analysis in the most favorable situation, i.e. missing data considered as success (e.g. for ORR, success is to be responder).

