7.1. Descriptive methods

- Descriptive analysis of qualitative and ordinal variables will comprise the count and the frequency of each category.

- Descriptive analysis of quantitative variables will be presented by the mean and standard deviation (SD) for the data that follows a Gaussian distribution and the median and range otherwise.
- The 95% confidence intervals will be presented for main endpoints. The ‘exact’ Clopper-Pearson confidence interval will be provided to assess 2-sided 95% confidence interval for main binomial proportions (e.g. ORR rate).
- The number of missing values will be reported in the results table for each variable.

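### Protocol 8.7: the ORR margin of at most ±8% for 140 patients fits a Wald interval, not the planned Clopper-Pearson interval, and leaves no room for patient loss (minor)

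*Protocol*

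**What the plan says.** Protocol 8.7 declines to size the study on PFS and uses the ORR on first-line sunitinib (SU) instead: "With 140 patients we will be able to assess the ORR to within a margin of error of at most" ±8%, with 95% confidence intervals. The condition follows: "This is based on the assumption that the ORR will be less than 37% as per the literature". No interval method is named. The 140 is the enrolment number (14 sites averaging 10 patients each), and no rate of unevaluable patients is given. The only other support for the sample size is that it lies within the range used in other studies.

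The analysis method is fixed elsewhere. Under Protocol 8.9 the ORR is "computed along with its 95% confidence interval using the Clopper-Pearson formula". SAP 7.1 agrees: the exact "Clopper-Pearson confidence interval will be provided to assess 2-sided 95% confidence interval for main binomial proportions", with ORR as its example.

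The denominator is described in several ways:

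- **Protocol 3.3.3:** "ORR is defined as the percentage of patients with confirmed CR or confirmed PR according to RECIST criteria v1.1". SAP Appendix 3 also uses a percentage of patients, with best response over the SU period.
- **SAP 4.1:** the efficacy population needs a dose of SU and at least 6 months of follow-up.
- **SAP 8.1.2:** the ORR role is stated for patients receiving second-line treatment after SU.
- **SAP 6:** "Regarding the descriptive analyses of each variable, it will be based on the available data". Counting missing responses as failures appears only as a sensitivity analysis: "analysis in the most unfavorable situation (i.e. missing data considered as failure").

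**The concern.** Protocol 8.7 words its margin as a maximum. A maximum should hold for the interval that will be reported and for the number of patients that will enter it. Neither is secured. The margin appears to come from a different and narrower interval than the planned one, and it uses every enrolled patient although the SAP contains a population rule that could remove some of them.

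What is at stake is limited. This is the only precision figure given for the sample size, so a reader of the report will compare the reported ORR interval with it. No decision rule depends on it, and Protocol 8.11 describes the study as hypothesis-generating.

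**Working it through.** **Inputs.** n = 140, margin 8 points, 95% confidence and ORR below 37% (Protocol 8.7); Clopper-Pearson interval (Protocol 8.9, SAP 7.1). The two-sided level is stated in SAP 7.1 and implied by the ± in 8.7. The condition on ORR is read as applying to the observed rate.

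**Step 1: reproduce the plan's figure.** Wald half-width = 1.96 × √(p(1 − p)/n).

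- At p = 0.37, n = 140: 1.96 × √(0.37 × 0.63/140) = 0.07998, that is 7.998 points.
- Inverted for 8 points: n = 1.96² × 0.37 × 0.63/0.08² = 139.9, so 140.

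The protocol's figure therefore comes out under Wald. Wilson at 37% would give 7.90, so Wald is the best match, although 8.7 does not say so. There is no slack: with 139 patients the Wald value at 37% is already 8.03.

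**Step 2: apply the planned interval.** For x responders among n, the lower limit is the 2.5% quantile of Beta(x, n − x + 1) and the upper limit is the 97.5% quantile of Beta(x + 1, n − x). The half-width is (upper − lower)/2. Since 52/140 = 37.14%, the last count below 37% is 51.

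| Responders of 140 | ORR | 95% interval | Half-width | Lower arm | Upper arm |
|---|---|---|---|---|---|
| 35 | 25.0% | 18.1% to 33.0% | 7.47 | 6.93 | 8.02 |
| 44 | 31.4% | 23.9% to 39.8% | 7.98 | 7.58 | 8.38 |
| 45 | 32.1% | 24.5% to 40.6% | 8.02 | 7.64 | 8.41 |
| 48 | 34.3% | 26.5% to 42.8% | 8.15 | 7.81 | 8.49 |
| 51 | 36.4% | 28.5% to 45.0% | 8.26 | 7.96 | 8.55 |

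The half-width is within 8 points up to 44/140 and above it from 45/140 to 51/140, by 0.02 to 0.26 points. The interval is asymmetric: the upper arm alone passes 8 points from 35/140.

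Reading the 37% as a true rate changes little. The expected Clopper-Pearson half-width at n = 140 is 7.98 at a true ORR of 32% and 8.05 at 33%.

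**Step 3: fewer than 140 in the denominator.** The documents give no loss rate, so the rates below are assumptions. The entry is the largest Clopper-Pearson half-width over all counts below 37%.

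| Assumed loss | Evaluable | Count at the maximum | Half-width | Wald at 37% |
|---|---|---|---|---|
| 0% | 140 | 51 | 8.26 | 8.00 |
| 5% | 133 | 49 | 8.49 | 8.21 |
| 10% | 126 | 46 | 8.72 | 8.43 |
| 20% | 112 | 41 | 9.26 | 8.94 |

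Against 8 points the excess is about 0.7 at 10% loss and 1.3 at 20%. Any loss breaks the bound at 37% under either method.

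**The case against.** The strongest reply is that nothing was miscalculated and nothing turns on the difference. This largely stands. The 8% is correct for the normal-approximation interval, 8.26 still rounds to 8% in the whole percentages that 8.7 uses, and the study is exploratory. The reply does not rescue the wording, because 8.7 claims an upper bound and the planned interval exceeds it over the range just below the ceiling that 8.7 itself assumes.

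A second reply is that loss may be small. Entry requires measurable disease, response is best response over the SU period, and SAP 6 says that mandatory web entry limits missing values, particularly for endpoints. If patients without a documented response count as non-responders, as a percentage of patients would suggest, n stays at 140 and only the method effect remains. This is fair, and it is why the figures for 5% to 20% are illustrations only. But SAP 6 makes missing-as-failure a sensitivity analysis, and the rule in SAP 4.1 would act regardless of how missing responses are coded.

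Three stronger readings are tempting, and the documents do not support them:

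- **That 8.7 contains an arithmetic error.** It does not. The fault is a mismatch with the planned interval.
- **That the SAP expects 20% or more of ORR data to be missing.** The sentence is a contingency: "In case of absence of 20% data and over, for a main parameter such as ORR rate, the Hot-deck imputation method could be used".
- **That hot-deck imputation will make the ORR interval too narrow.** It is optional, and the SAP does not say how the interval would be formed after it. Any coverage figure would rest on invented assumptions and does not bear on the margin in 8.7.

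**Conclusion.** Wrong as written, and minor. With all 140 patients evaluable, the planned interval exceeds the stated bound by at most 0.26 points, and only for observed rates from 32.1% to 36.4%. That part follows from the documents alone, taking the margin as half the interval's width. Judged by the longer arm, the excess starts at 25.0% and reaches 0.55 points (8.55 − 8).

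The second part is conditional. If the SAP 4.1 efficacy population is the ORR denominator and some patients have less than 6 months of follow-up, the denominator is below 140 and the bound fails by more. The documents do not say that this set applies to ORR. SAP 8.1.2 names a different group, patients with second-line treatment, which would also be smaller than 140. How much smaller either would be cannot be derived from the documents.

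A reader might infer that 140 patients are too few. The documents do not support that: they set no minimum precision beyond this sentence, and no test or decision depends on it.

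**What to change.** No change to enrolment.

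1. In Protocol 8.7, name Clopper-Pearson and restate the margin: for an ORR below 37% with 140 evaluable patients, a half-width of up to about 8.3 points, with the upper arm up to about 8.6 (8.55 rounded up). Add, marked as an illustration, half-widths of about 8.7 and 9.3 points under assumed losses of 10% and 20%.
2. Name the ORR denominator as all first-line SU patients, which is the group that 8.7 sizes. Reconcile SAP 4.1 and SAP 8.1.2 with it, and say whether patients without a documented response stay in as non-responders or leave the denominator.

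The cost is a slightly less favourable stated precision and an edit to both documents. Whether restating a precision figure needs a formal amendment is arguable. Protocol 4 asks for one for any change in the study plan, while Protocol 8.9 lets the SAP modify the protocol's plans and mentions an amendment only for major changes to primary endpoints.

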8.8. Data Management

The electronic data capture (EDC) system for this study is Viedoc, a web-based EDC system. It will be used to collect, monitor, and report clinical data as specified in the protocol.

Clinical staff will enter the data via a web-portal. All data collected via the eCRF will be reviewed by remote data monitors for clarity and completeness. Instances of missing or unclear data will be communicated back to the investigator for resolution. The database and data management plan will be generated according to approved specifications.

8.9. Data Analysis

Detailed methodology for summary and statistical analyses of data collected in this study will be documented in a Statistical Analysis Plan (SAP), which will be dated, filed and maintained by the sponsor. The SAP may modify the plans outlined in the protocol; any major modifications of primary endpoint definitions or their analyses would be reflected in a protocol amendment.

Demographic and other clinical characteristics of the patients will be summarized using the mean, standard deviation, median, minimum, and maximum values, for numeric variables such as age and duration of follow up and frequency distributions for categorical data such as gender. The median and 95% confidence intervals for the main outcomes PFS and TTF will be estimated using the method of Kaplan-Meier. The ORR for adv/mRCC patients receiving SU in the 1st line will be computed along with its 95% confidence interval using the Clopper-Pearson formula. Cox proportional hazard models may be used to explore the potential influences of baseline characteristics on PFS or TTF. A multiple logistic regression model can be used to assess the effect of prognostic variable on ORR.

Change in other variables such as Quality of life and weight at last visit as compared to the baseline will be assessed using the paired t-test at each visit in addition to computing mean differences along with 95% confidence intervals. Moreover, repeated methods can be used to look for trends over time and adjust for possible confounders.

All AEs occurring during the study will be considered as treatment-emergent, and the frequency of AEs will be summarized. Sub-group analyses of association between efficacy outcomes, safety measurements, and baseline factors will be performed for exploratory reasons as needed.

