3.5. Setting

The study will enroll patients according to the eligibility criteria in participating countries across Africa Middle East. The recruiting centers will be representative of each country involved in terms of care management systems, of size and of practices (at least when performing feasibility).

Any patient who meets the eligibility criteria will be invited to participate in the study with no selection by the investigators. The enrollment visit will be performed at the time of the patients' inclusion, after the patients' acceptance of enrollment in the study.

Data will come from medical records and will be collected in routine clinical practice. The enrollment visit will comprise a first section on patients' eligibility for every patient.

Follow-up will be ensured during visits in the context of usual patients' care management (non-interventional study). As long as the patients are treated with SU, AXI, other TKI (sorafenib, pazopanib everolimus, temsirolimus, other) or no further active treatment (supportive care), every visit to the center will be recorded. In accordance with ESMO guidelines and physicians clinical practice is real life, follow-up visits are approximately expected as below:

- During SU treatment: every 6 weeks (every cycle) with tumor assessment approximately every 3 months with respect to the clinical practice.
- When patients come off SU treatment: they will be followed-up every 6 months for survival until the end of the study.
- A deviation of +/- 6 weeks (1.5 months) is acceptable window for the follow-up visits.

Because of the inclusion criteria (patients being treated with SU in 1st line according to the approved therapeutic indication), the medication prescribed within the regular practice of the physician. Because of the non-interventional nature of the study, there will be no specific requirements in regards to the treatment process. The physician will determine dosage and duration of the treatment as guided by the local approved country. Prescribing information will be according to his assessment of the individual therapeutic needs of the patient.

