5. MILESTONES

Milestone	Planned date
Completion of feasibility assessment	Aug-2016
Start of data collection FSFV	Sep-2016
End of data collection, last subject last visit (LSLV)	Sep-2019
Final study report	Jan-2020

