8. RESEARCH METHODS

8.1. Study Design

OPTIMISE is an international (AfME), prospective, non-interventional, non-controlled, observational multicenter study.

Patients will be enrolled from several AfME countries including Algeria, Morocco, Tunisia, Egypt, UAE, Qatar & South Africa. Investigators will be specialists, in charge of adv/mRCC. These sites involved (at least when performing feasibility) will be representative of their respective country in terms of practice. Participating physicians will not be influenced in their decision making and routine proceedings in any way.

[figure not shown]
Primary outcome measure will assess PFS in patients receiving the SU and in patients receiving a second line treatment post SU; as well as TTF for patients with adv /mRCC.

Patients will be enrolled when they start a treatment with SU on 1st line. Patients enrolled at SU initiation, will be followed-up whatever the post SU-2nd line treatment is (AXI, other drugs, no further active treatment, (supportive care)). The possible 1st and 2nd line sequences of treatment under investigation (ie, patient pools) will be ([Figure 1](#)):

- SU-AXI.
- SU- other second line treatment (sorafenib, pazopanib, everolimus, temsirolimus, other).
- SU- not further active treatment (supportive care). The study will include a prospective data collection:
 - Prospective data will also be collected for all patients enrolled in the study at SU- 1st line level, irrespective of 2nd line treatment, or no further active treatment;
 - Prospective data in terms of medical treatment records, will be collected for all 2nd line patients.

The inclusion period of eligible patients is planned for 12 months, with minimum of 1 year follow-up period. Patients will be followed-up from their enrollment to the end of the study follow-up period.

Figure 1. Study Flow Chart

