7.4. Survival analysis methods

- The survival functions for PFS, TTF, TSF, and OS will be estimated with the Kaplan-Meier method. The survival function $S(t)$ is the probability that the event (treatment discontinuation, death or progression) does not occur before a specified time.
- This method will be applied to derive, survival curves, median event time and a 95% confidence interval for the median survival time (time at which half the analyzed patients have presented the event).
- Survival curves will give an idea of whether or not the groups are proportional (i.e. the survival functions are approximately parallel).
- For OS, the share of patients alive at 24 months will also be measured.
- The log-rank test of equality across strata will be used to compare survival curves for categorical variables (sub-groups of interest).
- For continuous variables, a univariate Cox proportional hazard regression will be used.
- For analyses of prognostic factors of survival time, multivariate Cox proportional hazard regressions will be performed.

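### Duration of follow-up is summarized as an ordinary numeric variable, so deaths shorten it and it tends to understate the follow-up available for overall survival

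*Protocol*

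**What the plan says.** Protocol 8.9 places follow-up time next to age among the patient characteristics, described by mean, standard deviation, "median, minimum, and maximum values, for numeric variables such as age and duration of follow up". SAP 7.1 has only a general rule for quantitative variables: they are "presented by the mean and standard deviation (SD) for the data that follows a Gaussian distribution and the median and range otherwise". Methods that allow for censoring are kept for the outcomes: "The survival functions for PFS, TTF, TSF, and OS will be estimated with the Kaplan-Meier method" (SAP 7.4). The visible text contains no reverse Kaplan-Meier estimate and no summary restricted to patients still alive. It does not define when follow-up starts or ends, and it does not name the analysis set for this summary.

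The length of follow-up can be read in three ways:

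- Protocol 8.1: "The inclusion period of eligible patients is planned for 12 months, with minimum of 1 year follow-up period". Closing at that minimum gives 12–24 months of potential follow-up.
- Protocol 8.4.1 and 8.5.3: the last numbered visit is at month 24.
- Protocol 5: data collection runs from September 2016 to September 2019, which is 36 months. With 12 months of accrual, patients followed to the end have 24–36 months. Protocol 3.5 supports this reading, since after sunitinib "they will be followed-up every 6 months for survival until the end of the study".

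Median OS and 24-month OS are listed among the secondary endpoints (Protocol 3.3.3).

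**The concern.** Age is fully observed in every patient, but follow-up time is not. For a patient who dies, the observed time is the survival time and says nothing about how long that patient would otherwise have been followed. The plain mean and median therefore fall when more patients die, even if nobody is lost.

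Readers normally use the follow-up figure to judge whether an OS median and a 24-month OS rate are well supported. The question is live here: data come from routine practice, Protocol 8.11 accepts that they may be incomplete, and the plan leaves the intended length of follow-up open to the three readings above. A figure that falls both with deaths and with losses cannot by itself tell a reader which of the two occurred.

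**Working it through.** **Plan's own figure.** There is none to reproduce. The documents give no expected follow-up, death rate or median OS for this study.

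**Inputs.** Potential follow-up C is taken from the documents: uniform on 12–24 months, fixed at 24, or uniform on 24–36. Assumed: exponential OS with median m of 12, 18, 24, 30 or 36 months, and no losses unless stated.

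**Formulas.** Observed time is the smaller of survival and C.

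- P(observed time > t) = 2^(−t/m) × G(t), where G(t) = P(C > t). For C uniform on a to b, G(t) is 1 up to a and (b − t)/(b − a) from a to b.
- The plain median is the time at which this product reaches 0.5. The plain mean is the area under it.
- Reverse Kaplan-Meier treats deaths as censored and so estimates G(t). Its median is (a + b)/2, that is 18, 24 and 30 months for the three designs.

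**Worked values.**

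- C 12–24, m = 18, t = 13.8: 2^(−13.8/18) = 0.588 and (24 − 13.8)/12 = 0.85. The product is 0.50, so the plain median is 13.8 against 18.
- C 24–36, m = 36, t = 26.1: 2^(−26.1/36) = 0.605 and (36 − 26.1)/12 = 0.825. The product is 0.50, so the plain median is 26.1 against 30.
- C fixed at 24, mean = (m/ln 2) × (1 − 2^(−24/m)). For m = 12 this is 17.31 × 0.75 = 13.0. For m = 36 it is 51.94 × 0.370 = 19.2.

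**Results in months, for m = 12 / 18 / 24 / 30 / 36.**

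| Potential follow-up | Reverse KM median | Plain median | Plain mean |
|---|---|---|---|
| 12–24 | 18 | 12.0 / 13.8 / 14.8 / 15.4 / 15.9 | 11.1 / 12.9 / 13.9 / 14.6 / 15.1 |
| Fixed 24 | 24 | 12.0 / 18.0 / 24.0 / 24.0 / 24.0 | 13.0 / 15.7 / 17.3 / 18.4 / 19.2 |
| 24–36 | 30 | 12.0 / 18.0 / 24.0 / 25.2 / 26.1 | 14.2 / 17.7 / 20.0 / 21.6 / 22.7 |

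Neither plain figure exceeds the reverse Kaplan-Meier median in any of these cells.

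**With losses.** With an assumed 10% lost per year (simulation), the reverse Kaplan-Meier median is about 17, 24 and 28.3 months in the three designs. The plain median runs over 10.4–14.9, 10.4–24.0 and 10.5–24.2.

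**Deaths against losses.** Take C 24–36. With median OS 15 and no losses, the plain median is 15. With median OS 30 and 20% lost per year, it is ln 2 / (ln 2/30 − ln 0.8/12) = 0.693/0.0417 = 16.6. The two look alike. Reverse Kaplan-Meier gives 30 and about 26.

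**The reported minimum.** The share dying before month 12 is 1 − 2^(−12/m): 50% at m = 12 and 21% at m = 36. A minimum below 12 months is therefore expected even when nobody is lost.

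**The case against.** The strongest reply is that the plan lists follow-up time as a descriptive characteristic and never says it will be used to judge maturity. A plain summary of observed time is a correct description of observed time. This stands, and it is why the plain summary need not be removed. It does not help a reader who takes the figure as the length of follow-up, which is how such a figure is normally read.

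Other planned output also carries part of the information. Deaths are reported as a proportion over treatment and along the study (SAP safety endpoints, just before 5.4), missing data are counted for each analysis (SAP 6), and losses are a monitoring item (Protocol 8.10). The one-year minimum can be checked from enrollment dates and the study end date. These points reduce the harm, but none of them yields a follow-up estimate free of deaths.

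Protocol 8.3 leaves variable definitions to the SAP, and SAP text between 4.2.1 and 5.4 is partly redacted or not shown. A definition of follow-up there cannot be excluded.

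A reader might infer more than the documents support:

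- **That the plain median simply equals median OS.** This needs no losses and a median OS no longer than the shortest potential follow-up. With 12–24 months of potential follow-up and median OS 18, it is 13.8.
- **That the figure largely reflects survival.** This depends on the death rate, which the documents do not give. The effect weakens as survival lengthens.
- **That the PFS data are misdescribed to the same degree.** The link is indirect, because PFS maturity depends on the number of events and on the timing of tumour assessments.
- **That the data would look more mature than they are.** The error runs the other way.

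**Conclusion.** The point holds as a low-cost improvement to reporting. The stated method mixes survival with observation time and tends to understate the follow-up available for median OS and 24-month OS. Across assumed OS medians of 12 to 36 months without losses, the plain median falls short by 18 down to about 4 months (potential follow-up 24–36), by 6 down to about 2 months (12–24), and by 12 down to 0 months (fixed 24). The zero arises when every patient has exactly 24 months, nobody is lost and median OS is at least 24 months; the mean is still about 5 to 7 months low there (24 − 19.2 and 24 − 17.3).

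These sizes rest on exponential survival, the assumed OS medians, uniform accrual, and a summary taken over all enrolled patients. The analysis set is not named, and the SAP 4.1 efficacy population, which requires at least 6 months of follow-up, would give a different figure. The Kaplan-Meier estimates of PFS, TTF and OS do not change.

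**What to change.** Add to SAP 7.4:

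- a definition of the start of follow-up (for example the first sunitinib dose, as for OS) and of its end, and the analysis set used;
- the median follow-up with 95% CI by reverse Kaplan-Meier, with deaths censored and last contact or data cut-off as the event;
- the number of patients lost before month 12 and before month 24.

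The summary in Protocol 8.9 may stay if it is labelled as observed time on study. It still describes how long patients were actually observed, for example for adverse events.

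The cost is a few lines in the SAP and one more Kaplan-Meier run on the same dates with the status code reversed, which SPSS can do. Protocol 4 requires an amendment for any change in the study plan, but Protocol 8.9 allows the SAP to modify the planned analyses and asks for an amendment only for major changes to primary endpoint definitions or their analyses. An addition to the SAP that leaves the protocol text in place is therefore enough.
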